1.4.3 Potential Benefits

Repetitive transcranial magnetic stimulation is a novel therapy that was cleared by the United States FDA in the autumn of 2008 for the treatment of MDD in adults who fail to achieve satisfactory improvement from one prior adequate antidepressant trial (see Appendix J2 for copy of Approval Letter). It is a promising alternative to treatments such as ECT or pharmacotherapy for patients presenting with treatment-resistant cases of MDD. The rTMS procedure is non-invasive, does not require anesthesia, and may be delivered in an outpatient setting.

2 Study Objectives

2.1 Primary Objective

2.1.1 Phase I

The primary objective of this study is to evaluate the safety and efficacy of rTMS as an adjunctive antidepressant therapy in a prospective, randomized, sham-controlled study in adolescents with MDD who have not responded sufficiently to at least one adequate

antidepressant medication trial. Stimulation will occur at a maximum of 120% magnetic field intensity relative to the subject's resting motor threshold (MT), at 10 pulses per second (10 Hz) for 4 seconds, with an intertrain interval of 26 seconds. During the treatment, intensity can be reduced, as needed, to 80% for tolerability. Upward titration with goal of return to maximum intensity (not to exceed 120% MT) will occur as tolerated by each participant. This is not expected to impact treatment response but may make the treatment experience more tolerable for the participating adolescents. Treatment sessions will last for 37.5 minutes (75 trains) to provide a total of 3,000 pulses per treatment session. A total of 30 treatments will be completed within 6-8 weeks of Phase I treatment initiation.

2.1.2 Phase II, Arm 1

The primary objective of this study is to evaluate the antidepressant benefit of 30 sessions of daily, active, open-label rTMS in Phase I nonresponders. Stimulation will occur at a maximum of 120% magnetic field intensity relative to the subject's resting motor threshold (MT), at 10 pulses per second (10 Hz) for 4 seconds, with an intertrain interval of 26 seconds. During the treatment, intensity can be reduced, as needed, to 80% for tolerability. Upward titration with goal of return to maximum intensity (not to exceed 120% MT) will occur as tolerated by each participant. This is not expected to impact treatment response but may make the treatment experience more tolerable for the participating adolescents. Treatment sessions will last for 37.5 minutes (75 trains) to provide a total of 3,000 pulses per treatment session.

2.1.3 Phase II, Arm 2

The primary objective of this study is to evaluate the sustained antidepressant benefit of 26 sessions of biweekly, open-label, active maintenance rTMS treatment for Phase I responders. Stimulation will occur at a maximum of 120% magnetic field intensity relative to the subject's resting motor threshold (MT), at 10 pulses per second (10 Hz) for 4 seconds, with an intertrain interval of 26 seconds. During the treatment, intensity can be reduced, as needed, to 80% for tolerability. Upward titration with goal of return to maximum intensity (not to exceed 120% MT) will occur as tolerated by each participant. This is not expected to impact treatment response but may make the treatment experience more tolerable for the participating adolescents. Treatment sessions will last for 37.5 minutes (75 trains) to provide a total of 3,000 pulses per treatment session.

2.2 Secondary Objective (MCR site only)

Secondary objectives of this study are to evaluate, by proton magnetic resonance spectroscopy (¹H-MRS) at 3 Tesla (3T), the following neurometabolic biomarkers:

- 1) Define regional specificity [anterior cingulate (AC) and left dorsolateral prefrontal cortex (L-DLPFC)] of cerebral metabolites (i.e. glutamate and glutamine) in adolescent depression.
- 2) Study whether specific neurochemical resonances are associated with response or remission of clinical depressive symptoms when rTMS is used to treat adolescent depression.

To accomplish these goals, the MCR site will utilize ¹H-MRS, a valuable, non-invasive method to study in-vivo brain biochemistry. Of the available imaging paradigms, ¹H-MRS is uniquely suited to investigate biochemical mechanisms of treatment action that are objectively

measurable and clinically relevant. As there is increasing interest in glutamatergic dysregulation in mood disorders, this project will utilize ^1H -MRS at 3T to study specific neurometabolic levels in the primary brain regions associated with major depressive disorder [anterior cingulate (Brodmann's areas 24a/b and 32) and L-DLPFC (Brodmann's 9/46)]. The goal of this aspect of the proposal is to evaluate whether anterior cingulate and prefrontal cortex neurochemicals (such as glutamine), quantified as a cerebrospinal fluid (CSF)-corrected absolute concentration percent change from baseline, are associated with clinical remission of depression when active rTMS is used.

3 Study Design

3.1 General Design

Treatment-site Localization Procedure:

A neuroradiologist at each site will review baseline MRI for potential exclusionary head and brain pathology. This localization procedure is the same procedure utilized preoperatively for neurosurgery – using a frameless stereotactic system (STEALTH – Mayo; Brainsight – MUSC). The optimal site of treatment, L-DLPFC, operationally defined as the gray matter of the superior frontal sulcus and portions of the superior and middle frontal gyri, containing Brodmann's areas 9 and 46. This location will be designated with a fiducial marker, along with clearly marked anatomic landmarks (nasion line, front and back of the ears) will be transferred to a lycra “swim-cap”. The treatment site noted on the swim cap will then be translated to the NeuroStar machine using a 2-dimensional coil template that will align the coil precisely over the designated treatment site. Once in place, treatment-site coordinates will be loaded into the device database so that subsequent treatments will be identically located. This process will forego the “guesswork” associated with moving the coil 5 or 6 cm anteriorly to the optimal motor threshold site – also known as the point at which the contralateral abductor pollicis brevis is consistently stimulated.

Phase I (Randomized, Double-Blinded):

Active Treatment

Adolescents randomized to active rTMS treatments will receive therapy using parameters that have been safely and feasibly utilized in adult randomized, controlled trials [7, 8] and the 2011 Wall et al. open-label trial in adolescents.[1] Stimulation will occur at 120% magnetic field intensity relative to the participant's resting motor threshold, at 10 pulses per second (10 Hz) for 4 seconds, with an intertrain interval of 26 seconds. During the treatment, intensity can be reduced, as needed, to 80% for tolerability. Titration and a return to maximum intensity (not to exceed 120% MT) will occur as tolerated by each participant. This is not expected to impact treatment response but may make the treatment experience more comfortable. Treatment sessions will last for 37.5 minutes (75 trains) to provide a total of 3,000 pulses per treatment session. A total of 30 treatments will be completed within 6-8 weeks of treatment initiation.

Sham Treatment

Adolescents randomized to sham treatments will have identical schedules, systematic assessments, and treatment approaches to their active treatment counterparts. Neither the adolescents nor the investigators (clinical raters or treaters) will know whether the treatment is active or sham in nature. The sham coil is identical in its appearance to the active coil. Furthermore, Neuronetics, Inc. has created an acoustic matching profile that renders the “sound” of the treatments virtually indistinguishable to participants or researchers. The acoustic

signal creates a painless percussive sensation that will be felt by the subject and will assist in simulating the active condition.

[figure not shown]
[figure not shown]
¹H-MRS methods (MCR site only)

Structural MRI and ¹H-MRS comparisons will be acquired for participants at the MCR site in two sessions lasting approximately 40 minutes each. A General Electric (GE) 3T Discovery MRI scanner running 22.1 software (or greater) and an 8-channel head coil will be used. The scanner is located in the Mayo Clinic - Main Mary Brigh MRI facility that is adjacent to the Generose Psychiatric Hospital (where the rTMS suite is located). A consistent MRS technician will be requested for each of the study scans as directed by [name]. Each MCR subject will have a baseline scan and additional scans at the completion of each treatment phase or at six months post treatment for subjects not electing to participate in Phase II. The maximum number of scans during the study will be three. Participants who discontinue the study will be offered a scan at the time of treatment withdrawal.

In order to ensure that the voxel location does not significantly change from scan to scan, a systematic approach to reference voxel positioning in all subjects is used. Briefly, an axial cut approximately 1 cm above the genu of the

corpus callosum showing a continuous view of the anterior and posterior horns of the lateral ventricles will be chosen as a reference slice (Figure 2). The center of a single 4-cm³ voxel (2-x-2 cm in-plane resolution by 1 cm thick) of predominantly gray (prefrontal) matter is centered on the frontal interhemispheric fissure. The voxel's posterior margin is placed immediately anterior to the genu of the corpus callosum in an area corresponding to the pregenual AC cortex (Brodmann areas 24a, 24b, and 32). A second 8-cm³ voxel will be centered in white matter deep to the L-DLPFC, operationally defined as the gray matter of the superior frontal sulcus and large portions of the superior and middle frontal gyri, containing Brodmann's areas 9 and 46. A long echotime (TE=80 ms) standard PRESS sequence (TR=2000 ms, number of acquisitions=128, bandwidth 500 Hz, 4096 points) will be used to measure glutamate and glutamine as well as measure the other metabolites. A second 2D J-averaged MRS sequence (TE=35-195 ms in 16 steps of 10 ms each, TR=2000, number of acquisitions=128, bandwidth 500 Hz, 4096 points) will also be used to optimally measure glutamate in each voxel. All MRS data will be processed using LCModel, a well-accepted, unbiased program for determining metabolite concentrations. A quantitative analysis of brain metabolites will be performed with a focus on the target metabolites. Anatomical image data will be segmented into gray matter, white matter, and CSF using a semiautomated thresholding technique developed internally at MCR ([name], [name], [name]). This segmented anatomical data will be combined with the spectroscopic data to obtain tissue-volume-corrected metabolite concentrations per accepted methods. This generates "absolute" (versus relative to creatine) metabolite concentrations in "institutional units" specific to our scanner and technique. These concentrations will then be used in the statistical analysis. An accepted data standard for healthy controls in these particular voxel locations will be used in the comparison.

Figure 2 – Voxel Placement examples
Top = AC; Bottom = L-DLPFC

Phase II (Non-Randomized, Open-label):

Arm 1: Acute Treatment (Nonresponder Cohort)

Participants who do not meet criteria for response (CGI-I rating of 3 or greater and/or a CDRS-R score of 28 or greater) following Phase I treatment will be offered the opportunity for 30 treatments using the known-active coil. The treatment parameters and methods of assessment will be identical to those in Phase I. The only difference will be that the coil used for Phase II will be active and known to the subject, family, and investigators. See Table 5 for schedule of assessments.

Arm 2: Maintenance Treatment (Responder Cohort)

Subjects who, at the completion of Phase I, meet clinical criteria for treatment response (CGI-I rating of ≤ 2 and CDRS-R score of < 28) will be offered the opportunity for 52 weeks of maintenance rTMS treatment. The treatment parameters will be identical to those in Phase I treatment except for the frequency of visits (biweekly) instead of daily. Clinical assessments will be offered monthly throughout the duration of the maintenance phase. One final follow-up assessment will be scheduled for six months post final treatment. See Table 6 for schedule of assessments.

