Duration of Exposure	
Phase I (Randomized, Blinded): For subjects randomized to the active treatment, stimulation will occur at a maximum of 120% magnetic field intensity relative to the subject's resting motor threshold (MT), at 10 pulses per second (10 Hz) for 4 seconds, with an intertrain interval of 26 seconds. During the treatment, intensity can be reduced, as needed, to 80% for tolerability. Upward titration with goal of return to maximum intensity (not to exceed 120% MT) will occur as tolerated by each participant. This is not expected to impact treatment response but may make the treatment experience more comfortable for the participating adolescents. Treatment sessions will last for 37.5 minutes (75 trains) to provide a total of 3,000 pulses per treatment session. A total of 30 treatments will be completed within 6-8 weeks of Phase I treatment initiation.
 
Phase II (Non-Randomized, Open-label): Acute Treatment (Arm 1): Subjects who did not achieve adequate clinical response to treatment in Phase I will be offered the opportunity to undergo acute rTMS treatment using the known-active therapy coil in Phase II. The treatment schedule and parameters will be identical to that in Phase I; i.e. daily stimulation will occur at a maximum of 120% magnetic field intensity relative to the subject's resting motor threshold (MT), at 10 pulses per second (10 Hz) for 4 seconds, with an intertrain interval of 26 seconds. During the treatment, intensity can be reduced, as needed, to 80% for tolerability. Upward titration with goal of return to maximum intensity (not to exceed 120% MT) will occur as tolerated by each participant. Treatment sessions will last for 37.5 minutes (75 trains) to provide a total of 3,000 pulses per treatment session. A total of 30 treatments will be completed within 6-8 weeks of Phase II treatment initiation.
 
Therefore, subjects who had been randomized to active treatment during Phase I and subsequently enroll in the Acute Treatment (Arm 1) of Phase II will receive a total of 60 active treatments using stated study parameters within the 12- to 16-week combined timeframes.
 
Subjects who were randomized to sham treatment during Phase I and subsequently enroll in the Acute Treatment (Arm 1) of Phase II will receive a total of 30 active treatments using stated study parameters within the 12- to 16-week combined timeframes.
 
Maintenance Treatment (Arm 2): Subjects who achieve adequate clinical response to treatment in Phase I will be offered the opportunity to undergo maintenance rTMS treatment using the known-active therapy coil in Phase II. Subjects will receive one treatment every other week for 52 weeks for a total of 26 treatments. Stimulation will occur at a maximum of 120% magnetic field intensity relative to the subject's resting motor threshold (MT), at 10 pulses per second (10 Hz) for 4 seconds, with an intertrain interval of 26 seconds. During the treatment, intensity can be reduced, as needed, to 80% for tolerability. Upward titration with goal of return to maximum intensity (not to exceed 120% MT) will occur as tolerated by each participant. Treatment sessions will last for 37.5 minutes (75 trains) to provide a total of 3,000 pulses per treatment session.
 
Combined duration of exposure for Phase I active/Phase II maintenance subjects would be 56 active treatments over 58 to 60 weeks. Combined duration of exposure for Phase I sham/Phase II maintenance subjects would be 26 active treatments over 58 to 60 weeks.

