3.4 Primary Safety Endpoints

The primary safety endpoint of this study is freedom from all treatment-related Unexpected Adverse Device Effects (UADEs) during the active treatment course and during the 6-month follow-up period. The definition of UADE is outlined in section 8.1 of the protocol.

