6.2.9 Monthly Post-Study Monitoring (+/- 2 weeks)

Monthly post-treatment monitoring may be conducted in-person (preferred), by telephone, or by videophone. Subjects for whom this scheduled may cause an undue time or travel burden may be given the option to complete abbreviated, safety-only screens for post-treatment months 1-5. If a subject reports a concern during the safety screen, the PI will determine whether they should be scheduled for a follow-up visit (in-person, telephone, or video phone) or whether more immediate action is needed.

Depression Assessments (optional):

- CDRS-R
- QIDS-A17-SR
- CGI-S
- CGI-I
- YMRS

Safety Assessments:

- C-SSRS
- Adverse event monitoring

Other Assessments (estimated 5 min):

- Vital Signs
- Change in medication/therapy monitoring

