6.3.2.3 Six-Month Follow-Up Visit (+/- 2 weeks from 6 months post Last Treatment)

Depression Assessments:

- CDRS-R

- QIDS-A17-SR
- CGI-S
- CGI-I
- YMRS

Cognitive Assessments:

- D-KEFS
- CAVLT-2

Safety Assessments:

- C-SSRS
- Adverse event monitoring

Other Assessments (estimated 5 min):

- Vital Signs
- Change in medication/therapy monitoring

Imaging Assessments:

- ^1H -MRS (MCR site only)

7 Statistical Plan

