- **Serious:** Serious problems or events that result in significant harm, (which may be physical, psychological, financial, social, economic, or legal) or increased risk for the subject or others (including individuals who are not research subjects). These include: (1) death; (2) life threatening adverse experience; (3) hospitalization - inpatient, new, or prolonged; (4) disability/incapacity - persistent or significant; (5) birth defect/anomaly; (6) breach of confidentiality; and (7) other problems, events, or new information (i.e. publications, DSMB reports, interim findings, product labeling change) that in the opinion of the local investigator may adversely affect the rights, safety, or welfare of the subjects or others, or substantially compromise the research data, **AND**
- **Unanticipated:** (i.e. unexpected) Unanticipated problems or events are those that are not already described as potential risks in the protocol, consent/assent document, the Investigator's Brochure, or not part of an underlying disease. A problem or event is "unanticipated" when it was unforeseeable at the time of its occurrence. A problem or event is "unanticipated" when it occurs at an increased frequency or at an increased severity than expected, **AND**

- Related: A problem or event is "related" if it is possibly related to the research procedures.

MUSC-Specific Definitions

Unanticipated Problem Involving Risk to Subjects or Others (UPIRSO)

An Unanticipated Problem is an event refers to any incident, experience or outcome that:

1. is unexpected (in terms of nature, severity or frequency) given: (a) the research procedures described in the protocol-related documents , such as the IRB-approved research protocol and informed consent document; and (b) the characteristics of the subject population being studied;
2. is related or possibly related to a subject's participation in the research; and
3. suggests that the research places the research subjects or others at a greater risk of harm (including physical, psychological, economic, or social harm) related to the research than was previously known or recognized.

Adverse Event Reporting Period

For this study, the treatment follow-up period is defined as six months following the last administration of rTMS.

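### Arm 2 has no scheduled safety contact between its post-treatment-26 visit and its six-month visit, while Phase I non-continuers and Arm 1 are checked monthly over the same safety window

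*Combined protocol and SAP*

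**What the plan says.** Section 3.4 defines the primary safety endpoint as freedom from treatment-related UADEs "during the active treatment course and during the 6-month follow-up period". Section 8.1 says "the treatment follow-up period is defined as six months following the last administration of rTMS". Neither section exempts any arm.

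Three follow-up schedules sit under that common window:

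- **Phase I subjects who do not enter Phase II.** Table 4 and Sections 6.2.8 to 6.2.10 give a post-treatment-30 visit, five monthly contacts and a six-month final visit. In Section 6.2.9 only the depression scales are optional. Subjects with a time or travel burden may have "abbreviated, safety-only screens for post-treatment months 1-5", and contact may be by telephone or videophone. In Table 4 the optional-assessment footnote is not attached to the C-SSRS or adverse event rows.
- **Arm 1.** Section 6.3.1 adopts Sections 6.2.3 to 6.2.10, and Table 5 repeats the five monthly contacts and the final visit.
- **Arm 2.** Section 6.3.2.2 gives a visit within 5 business days of the last session, with C-SSRS and mood scales. Section 6.3.2.3 gives one visit at six months, plus or minus two weeks. Section 3.1 agrees: "One final follow-up assessment will be scheduled for six months post final treatment". Section 3.2.3 mentions monthly C-SSRS, but a Table 6 footnote confines the monthly assessments to the maintenance period.

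Section 8.2 has the investigator ask about adverse events at each contact with the subject.

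**The concern.** The plan sets one six-month safety window but observes it at very different intensities. Because enquiry is tied to contacts, five months without a scheduled contact are five months without active enquiry. A non-serious event, or an episode of suicidal ideation, early in Arm 2 follow-up would be picked up mainly by recall at the six-month visit, or missed if the subject does not attend. Appendix E describes the C-SSRS short form as asking about recent ideation and behaviour, so one administration at six months is a weak substitute for monthly ones.

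At stake is the interpretation of the post-treatment safety tables. A lower event rate in Arm 2 follow-up could not be separated from less frequent questioning. The plan acknowledges in Section 1.4.2 that the long-term effects of rTMS are unknown. Arm 2 is the group with the longest calendar exposure.

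**Working it through.** **1. The plan's exposure figure.** The Study Summary gives Phase I as "A total of 30 treatments will be completed within 6-8 weeks of Phase I treatment initiation" and maintenance as "Subjects will receive one treatment every other week for 52 weeks for a total of 26 treatments".
- Sessions: 30 + 26 = 56.
- Weeks: 6 + 52 = 58, and 8 + 52 = 60.

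This reproduces the stated figure: "Combined duration of exposure for Phase I active/Phase II maintenance subjects would be 56 active treatments over 58 to 60 weeks". For a Phase I sham responder the active total is 26. For comparison, a Phase I active subject who enters Arm 1 can reach 30 + 30 = 60 active sessions in 12 to 16 weeks. Arm 2 therefore has the longest exposure in time but not the most sessions.

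**2. Scheduled safety contacts after the last session.**

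| Schedule | End-of-treatment visit | Monthly contacts | Six-month visit | Total |
|---|---|---|---|---|
| Phase I non-continuers | 1 | 5 | 1 | 7 |
| Arm 1 | 1 | 5 | 1 | 7 |
| Arm 2 | 1 | 0 | 1 | 2 |

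Tables 4 and 5 place follow-up at days 60, 90, 120, 150, 180 and 210. Taking day 30 of those tables as the last session, the contacts fall 30, 60, 90, 120, 150 and 180 days later. This agrees with the post-treatment months named in Section 6.2.9.

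**3. Longest scheduled gap.** Six months is taken as 182.6 days, and 5 business days as 0 to 7 calendar days.
- Arm 2, shortest: 182.6 − 14 − 7 = 161.6 days; 161.6 / 7 = 23.1 weeks.
- Arm 2, longest: 182.6 + 14 − 0 = 196.6 days; 196.6 / 7 = 28.1 weeks.
- Monthly schedules: nominally 30 days. If two adjacent windows of plus or minus 14 days are used at opposite extremes, 30 + 28 = 58 days.

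**4. Subjects affected.** The Study Summary gives 38 active and 37 sham subjects. Section 7.1 assumes response rates of 65% and 25%.
- Active: 38 × 0.65 = 24.7.
- Sham: 37 × 0.25 = 9.25.
- Total: 24.7 + 9.25 = 33.95, or about 34 of 75 offered Arm 2.

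This is an upper bound on those reaching follow-up under these rates, because some will decline or withdraw and the plan gives no estimate of how many.

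**The case against.** The case for leaving the schedule alone has real content.

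- **Arm 2 is not unobserved after its last session.** A reader of Section 3.1 alone might infer six months with no safety contact. Section 6.3.2.2 rules that out: a visit within 5 business days includes the C-SSRS, and Table 6 has adverse events assessed at every visit. The gap begins after that visit.
- **A risk peak after stopping is not established.** It is tempting to argue that relapse and suicidality cluster once maintenance ends. Section 4.4.1 says no risks of abrupt discontinuation are currently known, and Section 1.3 reports improvement lasting six months after treatment in a small open-label pilot. Unknown long-term effects do not amount to a known peak.
- **The primary safety endpoint is the least exposed.** UADEs are serious and previously unidentified, so they are less likely to be lost to recall. Worsening depression, suicidality and mania are already listed as anticipated risks, so they would generally not count as UADEs.
- **No planned test is shown to be biased.** Section 7.2 calls the Phase II analysis exploratory and mainly descriptive, with no test of Arm 2 against Arm 1. A reader might infer that the exact test of adverse events between treatment groups is distorted, because more active than sham subjects are expected to enter Arm 2. The plan does not say that this test includes Phase II follow-up, so that does not follow.
- **Passive routes exist.** Families are told to contact the study doctor about mood or behaviour changes, staff are available at all times, unresolved events are followed, and withdrawn subjects are offered assessments.
- **A lighter schedule could be defended.** Arm 2 completers are responders who have had about a year of regular visits, and the passages on Arm 2 agree with one another.

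These points remove the stronger readings. They do not remove the gap. The passive routes depend on the family to call, and the plan gives no reason for the difference in schedule.

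**Conclusion.** The point holds as a matter of unequal ascertainment. Over a six-month window common to all subjects, Arm 2 has 2 scheduled safety contacts against 7, and one unobserved stretch of about 23 to 28 weeks against a nominal month (at most about 58 days). Non-serious adverse events and suicidality in Arm 2 follow-up rest mainly on late recall. Descriptive post-treatment rates would not be comparable with the other schedules on two counts: the frequency of enquiry, and the split of the arms by response. The second would remain even with identical schedules.

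This is a design choice worth improving cheaply, not a contradiction in the plan. It does not touch the Phase I efficacy result, and the effect on the UADE endpoint is probably small. The gap rests on the visit windows as written and on six months being 182.6 days. The figure of about 34 subjects rests on the plan's assumed response rates and on full uptake and completion.

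**What to change.** Extend the existing abbreviated safety-only screen of Section 6.2.9 to Arm 2 for months 1 to 5 after the last session: C-SSRS, adverse event monitoring and changes in medication or therapy, by telephone or video. Add a monthly follow-up column to Table 6, and cite Section 6.2.9 in Sections 6.3.2 and 3.1.

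If the schedules are to stay different, give the reason and state in Section 7.2 that post-treatment event rates are not comparable across arms.

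The cost is a schedule amendment and at most five short calls per Arm 2 subject. With about 34 expected responders the upper bound is 34 × 5 = 170 calls, reached only if all enrol and finish. The screen is already part of the protocol, so no new instrument is needed.
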